## NON-INTERVENTIONAL (NI) STUDY PROTOCOL

### Study information

Title	Post-Approval Observational Cohort Study to Evaluate the Safety of the COMIRNATY 2023-2024 Formula in the United States
Protocol number	C4591062
Protocol version identifier	3.0
Date	18 March 2026
EU Post Authorization Study (PAS) register number	To be determined
Active substance	COVID-19 Vaccine, mRNA
Medicinal product	COMIRNATY 2023-2024 Formula
Country of study	United States
Research question and objectives	
Research question: What is the incidence of pre-specified safety events of interest among individuals who receive the COMIRNATY 2023-2024 Formula in the United States?
 
Phase 1
 
Primary objective:
 
 
To estimate the incidence of pre-specified safety events of interest following vaccination with the COMIRNATY 2023-2024 Formula compared to the incidence of these events during a control window (i.e., expected rates of these events).
 
 
Phase 2
 
Primary objective:
 
 
To estimate the incidence of pre-specified safety events of interest among individuals who receive the COMIRNATY 2023-2024 Formula compared to individuals with no recorded vaccination with the COMIRNATY 2023-2024 Formula.
 
 
Secondary objective:
 
 
To estimate the incidence of pre-specified safety events of interest among individuals who receive the COMIRNATY 2023-2024 Formula compared to individuals with no recorded vaccination with the COMIRNATY 2023-2024 Formula among subgroups of individuals with concomitant administration of a non-COVID-19 vaccine; immunocompromised individuals; individuals with specific comorbidities; individuals with prior SARS-CoV-2 infection;
 

090177e1a5be86fe\Approved\Approved On: 19-Mar-2026 15:57 (GMT)

PFIZER CONFIDENTIAL

	individuals with prior COVID-19 vaccination; pregnant women; pediatric subjects; and the elderly, if sample size permits.
Authors	
[name] Safety Surveillance Research Pfizer Inc. [contact] [contact]
 
[name] Senior Epidemiologist Optum Epidemiology [contact] [contact]
 
[name] Vice President, Epidemiology Optum Epidemiology [contact] [contact]

## 2. LIST OF ABBREVIATIONS

Abbreviation	Definition
ADEM	Acute disseminated encephalomyelitis
AE	Adverse event
AMA	American Medical Association
ASD	Atrial septal defect
AVSD	Atrioventricular septal defect
BEST	Biologics Effectiveness and Safety
CBER	Center for Biologics Evaluation and Research
CDC	Centers for Disease Control and Prevention
CHD	Congenital heart disease
CMS	Centers for Medicare and Medicaid Services
CI	Confidence interval
CIOMS	Council for International Organizations of Medical Sciences
COPD	Chronic obstructive pulmonary disease
COVID-19	Coronavirus disease 2019
CPT	Current Procedural Terminology
CVST	Cerebral venous sinus thrombosis
EC	Ethics committee
ED	Emergency department
EMA	European Medicines Agency
ENCePP	European Network of Centres for Pharmacoepidemiology and Pharmacovigilance
FDA	Food and Drug Administration
GPP	Good pharmacoepidemiology practices
HCPCS	Healthcare Common Procedure Coding System
HIV	Human deficiency virus
ICD-10	International Classification of Diseases, 10 th Revision
ICD-10-CM	International Classification of Diseases, 10 th Revision, Clinical Modification
IIS	Immunization Information Systems
IRB	Institutional Review Board
IP	Inpatient
LMP	Last menstrual period
MI	Myocardial infarction
mRNA	Messenger RNA
MS	Multiple sclerosis
NDC	National Drug Code
NSTEMI	Non-ST elevation myocardial infarction
ORD	Optum Research Database
OP	Outpatient
PAS	Post Authorization Study
PASS	Post-authorization safety studies
PDA	Patent ductus arteriosus

090177e1a5be86fe\Approved\Approved On: 19-Mar-2026 15:57 (GMT)

PFIZER CONFIDENTIAL

Abbreviation	Definition
PE	Pulmonary embolism
PS	Propensity score
RSV	Respiratory syncytial virus
SAP	Statistical analysis plan
SCRI	Self-controlled risk interval
SOP	Standard operating procedure
STEMI	ST elevation myocardial infarction
TAPVR	Total anomalous pulmonary venous return
US	United States
VAERS	Vaccine Adverse Event Reporting System
VSD	Ventricular septal defect

090177e1a5be86fe\Approved\Approved On: 19-Mar-2026 15:57 (GMT)

#### 4. ABSTRACT

**Title:** Post-Approval Observational Cohort Study to Evaluate the Safety of the COMIRNATY 2023-2024 Formula in the United States

**Version:** 3.0

**Date:** 18 March 2026

**Authors:** Optum: [name], Senior Epidemiologist, Epidemiology; [name], Vice President, Epidemiology; Pfizer: [name], Associate Director, Epidemiology, Safety Surveillance Research

**Rationale and background:** In September 2023, the FDA authorized the COMIRNATY 2023-2024 Formula, a monovalent mRNA vaccine targeting the Omicron variant XBB.1.5. More information is needed on whether the safety profile of the COMIRNATY 2023-2024 Formula remains consistent with the safety profile of the original formula in the overall population and in subpopulations of interest.

This non-interventional study is designated as a post-authorization safety study (PASS) and is a condition of authorization to the FDA.

##### **Research question and objectives:**

Research question: What is the incidence of pre-specified safety events of interest among individuals who receive the COMIRNATY 2023-2024 Formula in the United States?

##### Phase 1

Primary objective:

- To estimate the incidence of pre-specified safety events of interest following vaccination with the COMIRNATY 2023-2024 Formula compared to the incidence of these events during a control window (i.e., expected rates of these events).

##### Phase 2

Primary objective:

- To estimate the incidence of pre-specified safety events of interest among individuals who receive the COMIRNATY 2023-2024 Formula compared to individuals with no recorded vaccination with the COMIRNATY 2023-2024 Formula.

Secondary objective:

- To estimate the incidence of pre-specified safety events of interest among individuals who receive the COMIRNATY 2023-2024 Formula compared to individuals with no recorded vaccination with the COMIRNATY 2023-2024 Formula among subgroups of individuals with concomitant administration of a non-COVID-19 vaccine; immunocompromised individuals; individuals with specific comorbidities; individuals

with prior SARS-CoV-2 infection; individuals with prior COVID-19 vaccination; pregnant women; pediatric subjects; and the elderly, if sample size permits.

**Study design:** This is a non-interventional observational study utilizing an administrative claims database in the US. Phase 1 will utilize a self-controlled risk interval (SCRI) design, and Phase 2 will utilize a matched comparative safety cohort design.

**Population:** The source population for this study will consist of all individuals with at least one medical or pharmacy claim from 11 September 2023 through 31 March 2024. In Phase 1, individuals age  $\geq 6$  months will be eligible for inclusion if they receive at least one dose of the COMIRNATY 2023-2024 Formula from the date of product launch through 31 March 2024, have continuous medical and pharmacy insurance coverage in the 365 days prior to their vaccination date, experience a safety outcome of interest during a risk or control period, and do not experience the safety event of interest during the clean period prior to vaccination. In Phase 2, individuals age  $\geq 6$  months will be eligible for inclusion in the exposed cohort if they receive a dose of the COMIRNATY 2023-2024 Formula and have continuous medical and pharmacy insurance coverage in the 365 days prior to their vaccination. Individuals age  $\geq 6$  months will be eligible for inclusion in the unexposed cohort if they do not receive a dose of the COMIRNATY 2023-2024 Formula but do have a healthcare encounter and if they have continuous medical and pharmacy insurance coverage in the 365 days prior to their healthcare encounter. Individuals in the unexposed cohort will be matched to those in the exposed cohort if their healthcare encounter is in the same 14-day calendar period as the exposed individual's vaccination date and if they are in the same age group.

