#### 9.1.1. SCRI

Phase 1 will monitor the incidence rate of pre-specified safety events of interest in a general population of individuals who receive the COMIRNATY 2023-2024 Formula using an SCRI study design that tracks post-vaccination risk intervals and control (reference) periods for each vaccinated individual. Monitoring will be conducted during a pre-specified risk period immediately following vaccination, and the observed rate of events during this risk period will be compared to that of a control period temporally removed from the vaccination event. As depicted in [Figure 1](#), only individuals who receive the COMIRNATY 2023-2024 Formula will be included in the SCRI study ([Baker et al., 2015](#)). Within each individual, outcomes occurring during the risk interval will be compared with those occurring during the control period, in order to determine whether these outcomes occur more frequently immediately after vaccination as compared with a reference period. A washout period may be inserted between the risk interval and the control period to ensure that events relating to the vaccine are not incorrectly attributed to the control period. To ensure that observed outcomes are truly incident, a period free from the outcome of interest (clean period) may be required prior to vaccination.

090177e1a5be86fe\Approved\Approved On: 19-Mar-2026 15:57 (GMT)

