#### **9.2.4. Baseline Period**

The baseline period will consist of all continuously enrolled available time up to one year (365 days) prior to the vaccination date (SCRI) or cohort entry date (cohort study). Recognizing that narrower or specific windows of assessment may better capture select patient attributes of interest, specific covariates may be assessed using alternate time period(s). In this study, all individuals are required to have a minimum of 365 days of continuous health plan enrollment prior to the vaccination or cohort entry date (Sections 9.2.1.1 and 9.2.2.1), or continuous enrollment since birth if the vaccination or cohort entry date occurred at  $< 1$  year of age.

In both study designs, some or all of the baseline period will be used to exclude individuals with prevalent outcomes prior to vaccination or cohort entry date. This portion of the baseline period will be referred to as the ‘clean period.’ For a list of outcome-specific clean periods, please see [Section 9.3.2](#).

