**Table 2. Clean periods and risk intervals for safety outcomes of interest**

Outcome	Clean Period*	Vaccine Risk Interval*	Care Setting**
Acute disseminated encephalomyelitis	Days -28 to -1	Days 0 to 21	IP
Anaphylaxis	Days -30 to -1	Days 0 to 1	IP, ED
Bell's palsy	Days -183 to 0	Days 1 to 42	IP, OP
Cerebral venous sinus thrombosis	Days -365 to 0	Days 1 to 28	IP, OP
Convulsions/seizures, non-febrile	Days -42 to -1	Days 0 to 21	IP, OP
Encephalomyelitis	Days -183 to 0	Days 1 to 42	IP
Glomerulonephritis	Days -365 to 0***	Days 1 to 42***	IP, OP
Guillain-Barré syndrome	Days -365 to 0	Days 1 to 42	IP-primary position only
Herpes zoster	Days -270 to 0	Days 1 to 30	IP, OP
Immune-mediated myositis	Days -365 to 0***	Days 1 to 28	IP, OP
Immune thrombocytopenia	Days -365 to 0	Days 1 to 42	IP, OP
Kawasaki disease	Days -365 to 0	Days 1 to 21	IP, OP
Multi inflammatory syndrome	Days -365 to 0	Days 1 to 42	IP, ED
Multiple sclerosis	Days -365 to 0	Days 1 to 42***	IP, OP
Myocardial infarction	Days -365 to 0	Days 1 to 28	IP
Myocarditis/pericarditis	Days -365 to 0	Days 1 to 21	IP, OP

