#### **9.4.2. Optum Research Database**

The ORD is a proprietary research database containing eligibility and adjudicated pharmacy and medical claims data from a large US health plan affiliated with Optum. The individuals covered by this health plan are geographically diverse across the US. As early as 1993, medical and pharmacy claims data are available for 70 million individuals with both medical and pharmacy benefit coverage. In 2021, data were available for approximately 12.6 million individuals with medical and pharmacy coverage. Optum research activities use de-identified data from the research database. In limited instances, patient identifiers may be accessed where applicable law allows the use of patient-identifiable data, and when the study obtains appropriate approvals for accessing data that are not de-identified.

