The study power may be limited by the short duration of accrual and a limited follow-up period, particularly during Phase 1. Because the COMIRNATY 2023-2024 Formula was approved in September 2023, the study may be underpowered to conduct comparisons at the interim report stage.

Lastly, in all observational studies, treatment is not randomly assigned, and there is potential for residual confounding by factors not captured or poorly measured in claims databases. As often used in pharmacoepidemiology, a 1-year covariate assessment period prior to cohort entry will be used to control for potential baseline confounding in Phase 2. Use of a longer covariate assessment period may increase the capture of chronic conditions. However, most individuals with a chronic condition are expected to interact with the healthcare system at least once per year, suggesting that a 1-year covariate assessment period may be sufficient for capturing chronic conditions. Nevertheless, those without a visit in the 1-year baseline period may be missed. Additionally, prior COVID-19 vaccination in the previous year is an important potential confounder, but it could not be included in the propensity score model in Phase 2 due to potential positivity violations. Individuals who received a COVID-19 vaccine in the 270 days prior to cohort entry date will be excluded from the study, so by design, COVID-19 vaccination in the previous year is not an informative variable, as it would only capture COVID-19 vaccination in the 365 days to 271 days prior to receipt of the COMIRNATY 2023-2024 Formula. Finally, receipt of other vaccinations at baseline besides seasonal influenza vaccines and RSV vaccines will not be included in the propensity score model, which may result in residual confounding. To minimize this potential bias, the most common baseline procedure codes will be examined to identify additional baseline vaccinations that may be potential confounders. Baseline vaccinations other than seasonal vaccination or RSV that are identified during this process will be considered for inclusion in the propensity score model.

A strength of the current study is its incorporation of a self-controlled design, which eliminates the concern of confounding by time-fixed characteristics that vary across individuals. Similarly, in Phase 2, careful PS matching of the COMIRNATY and comparator cohorts is expected to minimize residual confounding in the cohort analysis. Finally, capture

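### Long-standing MS, and the chronic codes on two other outcome lists, can count as new disease after one code-free year; a longer look-back analysis is needed beside the 365-day one

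*Protocol*

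**What the plan says.** Section 9.1.1 gives the purpose of the clean period: "To ensure that observed outcomes are truly incident, a period free from the outcome of interest (clean period) may be required prior to vaccination". The abstract makes it an entry condition for Phase 1: cases must be people who "do not experience the safety event of interest during the clean period prior to vaccination". The closing paragraph of Section 9.2.2.2 applies the same outcome-specific exclusion in both phases.

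Table 2 gives the lengths: "Multiple sclerosis Days -365 to 0", "Glomerulonephritis Days -365 to 0" and "Immune-mediated myositis Days -365 to 0". A footnote says that the clean periods for glomerulonephritis and myositis could not be found in the literature and were modelled on other outcomes. All three outcomes accept inpatient and outpatient claims, and Appendix III makes a case from one code unless it says otherwise.

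Section 9.2.4 caps the window from which prevalent cases can be removed: the baseline is "all continuously enrolled available time up to one year (365 days) prior to the vaccination date (SCRI) or cohort entry date (cohort study"). Longer history exists at database level. Section 9.4.1 describes up to three years of prior data in the interim source, and Section 9.4.2 says of the Optum Research Database: "As early as 1993, medical and pharmacy claims data are available for 70 million individuals".

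Section 9.9 notes that the SCRI is weak for chronic outcomes such as MS and makes the cohort primary for them.

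**The concern.** The clean period is there to make outcomes incident. For a disease that persists for years, one year without a code does not do that. A patient diagnosed long ago who goes just over a year without a qualifying claim passes the screen and becomes a case at the next coded visit. Making the cohort primary for chronic outcomes does not help, because it uses the same Table 2 windows.

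A disease that began before Day 0 is not a new onset after vaccination. Such events add noise to both sides of the comparison, or bias if they arise unequally. At stake is whether a real increase in MS, or in the chronic part of the other two outcomes, reaches the signal rule in Section 9.3.2 (rate ratio above 3.0 with P below 0.01). Section 9.9 does not list prevalent disease counted as incident among the limitations.

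**Working it through.** The protocol states no event counts, incidence or power for these outcomes, so there is no figure to reproduce. What follows shows direction and sensitivity. Every value of k, D and v is an assumption.

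**SCRI.** Section 9.3.2.1 makes the control window as long as the risk window. Let k be the number of falsely incident events per true baseline event, equal in both windows. This means that re-coding of old disease is unrelated to vaccination. Then

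observed RR = (RR + k)/(1 + k).

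| k (assumed) | true RR 3 | true RR 4 | true RR 5 |
|---|---|---|---|
| 0.1 | 2.82 | 3.73 | 4.64 |
| 0.25 | 2.60 | 3.40 | 4.20 |
| 0.5 | 2.33 | 3.00 | 3.67 |
| 1 | 2.00 | 2.50 | 3.00 |
| 2 | 1.67 | 2.00 | 2.33 |

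Setting the observed ratio to 3.0 gives k = (RR − 3)/2. A true ratio of 4 stops exceeding the threshold at k = 0.5, and a true ratio of 5 at k = 1. A true ratio of 1 stays at 1, so this mechanism does not create a false signal in the SCRI.

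**Cohort.** Contamination may differ between exposed (kE) and comparator (kU):

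observed RR = (RR + kE)/(1 + kU).

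- True RR 3, kE = kU = 0.5: 3.5/1.5 = 2.33.
- True RR 3, kE = 2, kU = 0.5: 5/1.5 = 3.33.
- True RR 1, kE = 1, kU = 0.5: 2/1.5 = 1.33.
- True RR 1, kE = 0.5, kU = 1: 1.5/2 = 0.75.

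The protocol gives reasons for either direction. Comparators may enter at an outpatient visit (Section 9.3.1.2), and the clean period for these outcomes includes Day 0. Old disease coded at that visit therefore removes the comparator, which can leave kU below kE. If comparators have more visits later in follow-up, the effect runs the other way.

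**Length of look-back.** As an illustration, let D be the ratio of prevalence to incidence in years, v the number of coded visits per year, and L the code-free period in years. If visits occur at a constant random rate, k = D·v·exp(−v·L). Take D from 5 to 30 and v from 1 to 4:

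- L = 1: from 5 × 4 × exp(−4) = 0.37 to 30 × 1 × exp(−1) = 11.0. A true RR of 4 reads 3.20 to 1.25.
- L = 3: from 5 × 4 × exp(−12) = 0.0001 to 30 × 1 × exp(−3) = 1.5. A true RR of 4 reads 4.00 to 2.20.

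The formula counts every coded visit as an event and ignores the removal of people coded in both windows (Section 9.7.1.1), so it leans high. The gain at three years applies only to people enrolled that long.

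**The case against.** **The problem might seem to cover four lifelong diseases: MS, glomerulonephritis, immune-mediated myositis and immune thrombocytopenia.** The code lists do not support that. The glomerulonephritis list contains acute nephritic codes (N00.x). The myositis list contains myalgia and drug-induced myopathy. D69.3 is labelled neither acute nor chronic. The argument holds for MS and for the codes that are chronic on their face.

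**A reader might infer that the rate ratio is diluted throughout.** That follows only if re-coding is equal across windows or arms. It is a reasonable assumption in the SCRI, but the cohort direction is open. Prior-year visit counts are in the propensity model, which should narrow the gap between arms but does not settle its sign.

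**Section 9.9 might be read as conceding the point where it says that "those without a visit in the 1-year baseline period may be missed".** That sentence concerns covariates. It follows an argument that most people with a chronic condition have healthcare contact at least yearly. The argument limits the size of the problem, but a yearly contact is not a yearly claim carrying the disease code.

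**A reader might infer that decades of history lie unused for each patient.** The 1993 date and the 70 million people describe the whole database. Only 365 days are guaranteed per person, and Section 9.9 already notes history lost when people switch insurer.

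**The strongest objections are to replacing the primary definition.** Section 9.3.2.1 takes interval lengths from earlier vaccine studies, which cannot be checked here, and only the glomerulonephritis and myositis clean periods are marked as borrowed. An open-ended look-back gives people unequal histories. Section 7 also names relapsing or progressing MS among the reported events, and a longer screen removes those patients. A single G35 code does not separate a relapse from a routine visit, so the 365-day analysis does not measure relapse cleanly either. These points stand as reasons to keep the 365-day result and add to it. Finally, Section 9.3.2 allows record review for estimates approaching the threshold. That softens a near miss, but it is optional.

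**Conclusion.** The concern holds for MS and for the clearly chronic codes on two other lists, such as N03.x, N07.A and inclusion body myositis. The plan aims at incident disease, screens for at most 365 days, accepts one code as a case, and does the same in the analysis that it calls primary for chronic outcomes.

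In the SCRI, on the assumption that re-coding is unrelated to vaccination, the bias is toward 1. At k = 0.5 (assumed) it brings a true ratio of 4 down to 3.0, which misses the signal rule. In the cohort the direction cannot be stated. The documents give no values for k, D or v, so the real size is unknown and may be small if most patients are coded every year. They support an added analysis and a stated limitation, not a finding that the planned results are diluted by a known amount.

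**What to change.** - For MS, and for the chronic-code subset of glomerulonephritis and immune-mediated myositis, add a pre-specified analysis in both phases. It excludes anyone with the outcome code in any available enrolled history before Day 0, with the existing 365-day minimum kept.
- List the chronic subset by code in Appendix III. G72.41 appears there under three different labels, so the text must say which condition is meant.
- Report length of prior enrolment by arm in the cohort, and interpret the result beside the 365-day result, which stays as planned.
- Add prevalent disease counted as incident to Section 9.9. State that the expected bias is toward 1 in the SCRI if re-coding is unrelated to vaccination, and of unknown direction in the cohort.

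Costs: look-back length varies between people. In the SCRI this cannot differ between a person's own windows, but in the cohort it can differ by arm, and reporting enrolment length shows such an imbalance without correcting it. Some matched sets are lost, because Section 9.7.2.1 also drops the matched comparators of excluded people. Section 9.6 plans one extraction per report, so earlier history must be in that extract or a further extraction is needed. The milestones put the analytic dataset at 31 August 2025 and the final report at 30 April 2026, so the analysis should be fixed in writing before the outcome results are examined.
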